- 11. Patient belongs to the study site personnel directly involved in the study or is the closest relative of the study investigator. "Immediate relative" means husband, wife, parent, son, daughter, brother, or sister (regardless of whether they are natural or adopted).
- 12. Patient who works for OOO "NPF "MATERIA MEDICA HOLDING" (i.e. i.e. they are employees of the Company, temporary employees on a contract basis or appointed officials responsible for conduction of the study or their immediate family members).

Criteria for Withdrawal or Termination

- 1. Screening failure.
- 2. Laboratory-confirmed case of SARS-CoV-2 infection (with or without symptoms).
- 3. Inability or refusal of the patients to comply with the protocol requirements.
- 4. Use of any medication listed in the section "Prohibited concomitant medications".
- 5. An adverse event requiring discontinuation of the study.
- 6. Participant's decision to complete the study early due to lack of the therapy efficacy or any other reasons.
- 7. Pregnancy.
- 8. Cases not specified by the protocol when, according to the investigator's opinion, further participation in the study harms the patient.
- 9. Eligibility error.
- 10. Participation in any other clinical trial.
- 11. Unblinding.

Number of subjects

Study stage before adaptation:

1268 participants will sign the informed consent.

At least 1206 participants will be randomized.

Study stage after adaptation⁴:

Additional 0 to 2332 participants will sign the informed consent.

Therefore, additional 0 to at least 2214 participants will be randomized.

The total maximum sample size will be: 3600 participants will sign the ICF, n=**3420** of which will be randomized.

⁴ Refer to the section Statistical Methods

Interim analysis

An "unblinded" interim analysis for 85% of the sample (0.85 information, 485 PP participants each) is planned in the protocol. It is assumed that the study can be stopped due to the rejection of the null hypothesis with the O'Brien-Fleming type I error spending function. Based on the results of this analysis (if the stopping parameters are not achieved), it is assumed that the study will be adapted to determine the required additional sample size.

Treatment

Group 1

Name of the medicinal product: Ergoferon

Active ingredient: affinity purified antibodies to human gamma interferon – 0.006 g*

affinity purified antibodies to histamine - 0.006 g*

affinity purified antibodies to CD4 - 0.006 g*

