Full Analysis Set. This sample includes all the enrolled patients, except for those who have experienced at least one of the following events:

- 1) non-compliance with inclusion/exclusion criteria;
- 2) patient did not take any dose of study drug;
- 3) absence of any patient data after administration of study drug.

Patients who had at least one of the listed events may be excluded from the analysis.

This sample, the most consistent with the "Intention-to-treat" principle, will be used for the *Intention-to-treat analysis (ITT analysis)* of the the study therapy efficacy.

Per protocol set. This sample includes all the patients who received full protocol therapy, completed all the scheduled visits. This sample will be used for *Per Protocol analysis (PP-analysis) of the the study therapy efficacy. Per Protocol set* will not include the patients whose data are fully or partially invalid for analysis due to a protocol deviation.

Protocol deviations resulting in full or partial data invalidity:

- 1. Violation of visit schedule.
- 2. Inappropriate distribution/issue of the study drug.
- 3. Prescription of prohibited therapy.

- 4. Increase or decrease of 25% or more in the amount of study therapy received.
- 5. Inability to assess patient's objective compliance (adherence to therapy) according to the formula (e.g. loss of packaging).
- 6. Major discrepancies between source documents and CRF detected during monitoring or other authorized inspection.
- 7. Violations of the Informed consent procedure.
- 8. Non-compliance with the clinical study protocol procedures.
- Inability to collect all patient's data used for evaluation of the study endpoints (e.g. lack of entries in source documents required for verification of inclusion/exclusion criteria, safety and efficacy criteria).
- 10. Any other protocol deviations that fall under definition of "significant deviation."

Data treatment and all statistical calculations under the protocol will be made using SAS-9.4 statistical software.⁵

Evaluation of sample size

The sample size has been assessed on the basis of the following rules and assumptions:

- 1. Statistical provisions.
 - 1.1 the power of the statistical tests " $P = (1 \beta)$ " is assumed to be 80% (the probability of correct rejection of the null hypothesis is 0.8);
 - 1.2 the probability of a type I error " α " is allowed to be less than 5% (the probability of the erroneous acceptance of an alternative hypothesis is less than 0.05);

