 - 1.3 statistical criteria of intergroup comparisons will be two-sided unless otherwise specified;
 - 1.4 ratio between Ergoferon and Placebo sample sizes is 1:1 (1 Ergoferon patient per 1 Placebo patient);
 - 1.5 an "unblinded" interim analysis with possibility of early stopping due to the effectiveness on 85% of the sample is planned in the protocol. Error spending function O'Brien-Fleming;
 - 1.6 sample size can be adjusted after the interim analysis based on the estimated conditional power (at the same time as the interim analysis is conducted);
 - 1.7 statistical null and alternative hypotheses regarding the superiority of Ergoferon over Placebo for the dosing regimen used:

Primary endpoint:

H₀: $OR_{12} = 1$

⁵ Holder of license: OOO "NPF "Materia Medica Holding", No. 70100045.

Ha: OR1 $2 \neq 1$

where OR_{12} – odds ratio of an event occurring between the Placebo and Ergoferon.

The following SAS code was used to determine the required sample size⁶:

proc seqdesign errspend;

design nstages = 2 info = cum (0.85 1) method (alpha) = obf alt = twosided stop = reject alpha = 0.05 beta = 0.2 samplesize model = twosamplefreq (nullprop= $0.03 \text{ prop}=0.005^7$)

run

1.8 the final sample size is calculated with the following formula:

$$\mathbf{N} = \mathbf{N}_{PP} / (1 - \mathbf{K}_{B}),$$

where N – final sample size; N_{PP} – sample size value in c. 1.7, i.e. scheduled number of patients completing the study per protocol; K_B – withdrawal rate.

2. Assumptions about the expected effects of the clinical study:

It is assumed that the **odds ratio** for the occurrence of an event will be not less than 0.162 in favor⁸ of Ergoferon (as part of the adaptation process, a possible deterioration in the magnitude of the prediction of the effect is assumed to be up to 0.55).

Population frequency: assumed to be 3%⁹.

Therefore, the required size for each group is 570^{10} patients (PP sample). Considering the potential dropout of about 10% patients during the study for various reasons¹¹, at least 1268 patients (634 in each group) will be required to sign informed consent, of which 1206 patients will be randomized (603 in each group) (see cl. 1.8, the final total withdrawal rate will be ($K_B = 0.1$).

⁶ Minimum size for this study.

⁷ Equivalent to effect size OR=0.162 (smaller is better).

 $^{{}^{8}}$ OR = Odd_{tr}/Odd_{pl} – the higher, the greater the chance in Ergoferon group compared to the Placebo group.

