 ⁹ Rare event frequency assessment, is a population parameter and can be overestimated in a blinded interim analysis.
 ¹⁰ Minimum size.

¹¹ Of them patients dropped out during the screening process (5%)

Sample Size Adaptation

It is intended to adapt the sample size during the study in accordance with the following algorithm¹²:

 During the planned interim analysis (if the study was not completed due to rejection of the null hypothesis based on the interim analysis cutoff), the conditional power is calculated using the formula:

$$CPower = 1 - \Phi\left(\frac{z_{\alpha} * \sqrt{N_{min}} - z_{1} * \sqrt{N_{1}}}{\sqrt{N_{min} - N_{1}}} - \frac{z_{1} * \sqrt{N_{min} - N_{1}}}{\sqrt{N_{1}}}\right)$$

where Z_1 is the value of the Z-statistic obtained at the interim analysis on N_1 of the first patients from N_{min} (the minimum sample size of the study);

Za = 2.0255 (the value of statistics for the final analysis, taking into account the presence of an interim analysis);

- $\Phi_{(x)}$ the probability value of event **X** for the standard normal distribution ($\sigma = 1, \mu = 0$).
- 2) The maximum allowable increase in sample size is assumed to be no more than 3240^{13} .
- 3) Taking into account the above, one of the adaptation scenarios will be selected.
- 4) Optimistic scenario (conditional power CPower > 0.8, or equivalently Z₁ > 2.168): sample size does not change (N_{final} = N_{min}).
- 5) Medium scenario (conditional power 0.3¹⁴ < CPower < 0.8, or equivalently value 1.6815 < Z1 < 2.168): the sample size changes according to the formula:

$$N_{final} = N_1 + \left(\frac{N_1}{z_1^2}\right) * \left(\frac{z_{\alpha} * \sqrt{N_{min}} - z_1 * \sqrt{N_1}}{\sqrt{N_{min} - N_1}} + z_{\beta}\right)^2$$

- 6) Pessimistic scenario (conditional power CPower < 0.3, or, equivalently, value Z1 < 1.6815): sample size does not change (N_{final} = N_{min}).
- 7) The final statistical analysis is carried out with the critical statistical values obtained by estimating the minimum sample size ($Z\alpha = 2.0255$).

Statistical criteria

All the statistical calculations will be performed using two groups of statistical criteria:

¹² Adaptive Increase in Sample Size when Interim Results are Promising: A Practical Guide with Examples Cyrus R. Mehta1,2, Stuart J. Pocock3 STATISTICS IN MEDICINE Statist. Med. 2000; 00:1–6

¹³ Taking into account withdrawal - up to 3600

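### The efficacy stop and sample-size adaptation are counted in per-protocol participants; no set is named primary, no ITT result is required before stopping, and set membership is not fixed before unblinding

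*Combined protocol and SAP*

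**What the plan says.** The Interim analysis section of the protocol says that an unblinded "interim analysis for 85% of the sample (0.85 information, 485 PP participants each) is planned in the protocol". This is the only early stop. It is for rejection of the null hypothesis, and the same look drives the sample-size adaptation.

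Under Evaluation of sample size, the 570 per arm is labelled the PP sample, and item 1.8 defines N_PP as the sample-size value, "i.e. scheduled number of patients completing the study per protocol". Under Sample Size Adaptation, item 1, Z1 "is the value of the Z-statistic obtained at the interim analysis on" the first N1 patients of N_min. No analysis set is named there.

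The Samples section defines two efficacy sets.

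- **FAS.** "This sample, the most consistent with the 'Intention-to-treat' principle, will be used for the" ITT analysis of efficacy. It leaves out ineligible participants, those who took no drug and those with no data after dosing.
- **PP set.** It requires full therapy and every scheduled visit. Deviations that remove data include visit violations, prohibited therapy, a change of 25% or more in treatment received, non-compliance with protocol procedures (item 8) and, in item 10, "Any other protocol deviations that fall under definition of" a significant deviation.

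The text does not say which set governs the stop, the conditional power, N_final or the final test at 2.0255. It also does not say when membership of either set is fixed.

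**The concern.** In a superiority trial, a test on a set defined by what happens after randomisation loses the protection of randomisation. Here some exclusions can be linked to the endpoint. Prohibited drugs include antivirals and systemic corticosteroids, which a participant who falls ill might take. Items 8 and 10 are open-ended and leave room for judgement.

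Three gaps compound this.

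- The plan's ITT analysis has no role in the stopping decision, so a trial stopped at 85% could have met its alpha-controlled boundary only in the selected subset.
- If the PP count sets only the timing of the look, the set for Z1 is unspecified and could be chosen after results are seen.
- Without a lock on membership, a participant could be counted at the interim and excluded at the final analysis, or the reverse. The limit of 2.0255 assumes that the interim data are nested in the final data.

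Few cases are expected, so a single in/out decision can matter.

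**Working it through.** **Inputs from the plan.** Placebo rate 3%, Ergoferon rate 0.5%, two-sided alpha 0.05, power 80%, looks at information 0.85 and 1 with O'Brien-Fleming spending, 570 PP per arm (485 at the interim), 603 randomised per arm, final limit 2.0255.

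**1. The plan's own figures.**
- OR = (0.005/0.995)/(0.03/0.97) = 0.1625; ln OR = −1.817.
- n = (1.960 + 0.842)² × [1/(0.03 × 0.97) + 1/(0.005 × 0.995)] / 1.817² = 559.4. Multiplied by the two-stage inflation of 1.01885 this is 569.98, so 570 reproduces.
- 570/0.9 gives 634 consented per arm; 634 × 0.95 = 602.3, stated as 603.
- Interim limit: 2.0255/√0.85 = 2.197.
- Conditional-power formula with N1 = 970, N_min = 1140: Z1 = 2.168 gives 0.800 and Z1 = 1.6815 gives 0.300, as printed.

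**2. Do the printed limits show that Z1 is a PP statistic?** No. With randomised counts, N1 = 1026 and N_min = 1206, the same two values of Z1 also give 0.800 and 0.300. The limits depend only on the ratio: 970/1140 = 0.851 and 1026/1206 = 0.851.

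**3. Size of the look.**
- Expected PP cases: 485 × 0.03 + 485 × 0.005 = 14.55 + 2.43, about 17.
- Planned loss between randomisation and PP: (603 − 570)/603 = 5.5%, or 66 of 1206.
- At the interim: 970 × 1206/1140 = 1026 randomised, so 1026 − 970 = 56 lie outside the PP count. That is over three times the expected cases.

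**4. One classification.** Pooled Z (an assumption; the plan does not give the form of Z1), Z = [(b − a)/485] / √[p̄(1 − p̄) × 2/485], with a Ergoferon and b placebo cases and p̄ = (a + b)/970:
- 14 vs 5: 0.01856/0.00890 = 2.085. No stop; this falls in the medium scenario (1.6815 to 2.168), where the sample is enlarged.
- 14 vs 4: 0.02062/0.00867 = 2.379. Stop.

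**5. Two-way sensitivity.** Exact binomial enumeration, 485 per arm throughout, probability of Z at or above 2.197 in Ergoferon's favour:

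| True rates (placebo vs Ergoferon) | As counted | One Ergoferon case removed | One placebo case removed |
|---|---|---|---|
| 3% vs 0.5% | 0.831 | 0.909 | 0.770 |
| 3% vs 1% | 0.528 | 0.651 | 0.451 |
| 3% vs 3% | 0.0138 | 0.0246 | 0.0091 |

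With no effect, removing one case from each arm gives 0.0169. A log-OR Z with 0.5 added to each cell gives 0.0098 as counted and 0.0176 with one Ergoferon case removed.

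**6. Price of testing all randomised.** Assume the participants outside PP get no benefit. Take their share as 5.5% (the plan's loss after randomisation) to 10% (its total withdrawal rate).
- 5.5%: Ergoferon rate 0.945 × 0.005 + 0.055 × 0.03 = 0.0064; OR 0.207; the formula in step 1 gives 621 per arm.
- 10%: rate 0.9 × 0.005 + 0.1 × 0.03 = 0.0075; OR 0.244; 679 per arm.
- Chance of crossing at the interim with 513 per arm: 0.86 undiluted, 0.78 and 0.71 diluted.

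**The case against.** The strongest reply is that the plan does not say the decisions are made on the PP set. The count of 485 PP per arm may set only the size and timing of the look, and sizing on evaluable participants does not by itself fix the analysis set. This stands: PP is the likelier reading, because no other set is mentioned there, but it is an inference, and step 2 shows that the printed limits do not settle it. Under the other reading the governing set is unspecified, and the remedy is the same.

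A reader might infer that the plan has no ITT test. That is wrong: the Samples section plans an ITT efficacy analysis on the FAS. What is missing is any rule giving it primacy or requiring it before a stop.

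A reader might also take the rise from 1.4% to 2.5% as the bias from using PP. It is not. Nothing in the plan suggests that exclusions favour one arm, and they are applied in a double-blind trial. If exclusion at 5.5% were unrelated to outcome (assumption), about 513 × 0.03 × 0.055 = 0.84 placebo cases would be lost, and at least one Ergoferon case in only about 13% of trials (513 × 0.005 × 0.055 = 0.14; 1 − e^−0.14 = 0.13). On average that works against Ergoferon.

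The document calls itself a protocol summary, so a blinded data review may be described elsewhere. That is possible, but the text available contains none. Finally, the FAS is not all randomised, so moving to it only partly restores the randomised comparison.

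**Conclusion.** The point holds as a gap in specification with a real consequence. The stop and the adaptation are sized and described in PP participants. The planned FAS analysis has no stated role in them, and membership is not fixed before unblinding.

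On the natural reading, superiority could be declared on about 17 expected cases, with about 56 randomised participants outside the set. One classification can move the trial from enlarging to stopping (14 vs 5 against 14 vs 4). The figures rest on the plan's rates and a pooled Z. The sensitivity runs both ways, with a no-effect crossing chance of 1.4% becoming 2.5% or 0.9%. It shows fragility and does not measure bias. The plan should be changed before the interim look, but the point does not by itself show that a positive result would be false.

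**What to change.** 1. In Interim analysis, Samples and Sample Size Adaptation, name one primary set for Z1, the stop, the conditional power, N_final and the final Z. It should be the FAS or, better, all randomised participants, taken in randomisation order: about the first 1026 randomised, expected to yield 970 PP. Report the PP result as supportive.
2. State that endpoint cases stay in every set. Study design ends a confirmed case's participation early, while the PP definition asks for all scheduled visits; read literally, this would drop the cases.
3. Lock FAS and PP membership of the interim participants at a blinded review before unblinding, and do not reopen it.
4. Count N1, N_min and the cap in one unit. In randomised participants these are about 1026, 1206 and 3420; the plan's cap of 3240 is the PP counterpart (3600 × 0.9 = 3240; 3600 × 0.95 = 3420). The limits 1.6815, 2.168 and 2.0255 stand while N1/N_min stays at 0.85.

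**Cost.** Wording and one blinded review, plus, if all randomised are used, a rule for participants with no data after dosing. No extra enrolment is proposed. The downside should be disclosed: if the excluded 5.5% to 10% get no benefit, 80% power would need about 621 to 679 per arm against 603 randomised. The stated power should therefore be described as applying to the PP effect.

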The study will enroll adult participants of either gender aged ≥ 18 years who receive a COVID-19 vaccine. A participant signs a participant information sheet (Informed Consent Form) to participate in the clinical trial on the day of administration the first dose of the Gam-COVID-Vac (Sputnik-V) vaccine. The physician evaluates the participant's eligibility for inclusion in the study. A rapid test for SARS-CoV-2 (BIOCREDIT COVID-19 Ag)² is carried out.

If the participant meets all inclusion criteria and does not have any non-inclusion criteria, then he is included in the study, the doctor fills out the primary medical documentation.

After inclusion in the study (Day 1, Visit 1), the participant is randomized into one of two groups: participants in group 1 receive Ergoferon according to a preventive regimen for three weeks, participants in group 2 receive Placebo for three weeks.

On a day of administration of the second Gam-COVID-Vac dose³ (Day 22, Visit 2 + 3 days), a rapid SARS-CoV-2 test (BIOCREDIT COVID-19 Ag) is performed.

After administration of the second dose of the vaccine, the participant is observed for 2 weeks. After 2 weeks, Visit 3 (telephone visit) is conducted to interview the participant about their health status (absence/presence of ARVI symptoms).

All participants are provided with classic axillary temperature thermometers. The study uses an electronic diary to record any possible deterioration in the participant's condition (if applicable) to assess efficacy, safety and reporting of adverse events. The investigator instructs the participant to complete the diary. Each participant will receive an SMS reminder once a week: "If you have any symptoms of the disease, record them in the diary. The investigator will contact you."

If within five weeks of observation the participant develops symptoms of acute respiratory viral infection (increased body temperature to febrile/subfebrile values, weakness, headache, chills, cough, sore throat, other symptoms), then the study investigator performs an unscheduled visit, during which swabs are taken from the nasopharyngeal and oropharyngeal mucosa for PCR (RT-PCR) test (in the central laboratories).

If at Visits 1 or 2 a participant without ARVI symptoms has a positive rapid test result for SARS-CoV-2, his/her oropharyngeal and nasopharyngeal swabs are also collected for PCR testing (in the central laboratory).

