² If the participant tests positive for SARS-CoV-2, he/she is not enrolled in the study. The investigator's approach should be in compliance with the current version of the guidelines "Prevention, diagnosis and treatment of a new coronavirus infection (COVID-19) by the Ministry of Health of the Russian Federation.

³ Contraindications for the second dose of the vaccine: Severe post-vaccination adverse events (anaphylaxis, severe generalized allergic reactions, convulsive disorder, fever (\geq 40°C), etc.) following the injection of the first dose of the vaccine.

If a laboratory-confirmed case of SARS-CoV-2 infection (with or without symptoms) is detected, the participant prematurely completes the study as having reached the primary endpoint.

If the PCR test for SARS-CoV-2 is positive, in accordance with the requirements of Rospotrebnadzor, the information is transferred to the health care facility to which the participant is attached, where he will be provided with the necessary medical care (according to current standards). Health care facility employees report data on COVID-19 cases (in accordance with the recommendations of the Ministry of Health of the Russian Federation and the rules of health care facilities).

Possible post-vaccination symptoms;

- general (flu-like syndrome characterized by chills, fever, arthralgia, myalgia, asthenia, malaise, headache) and local (pain at the injection site, hyperemia, swelling) symptoms that develop on the first-second day and resolve within three days;
- nausea, dyspeptic disorder, loss of appetite;
- enlarged regional lymph nodes;
- allergic reactions;
- transient increase in serum levels of liver transaminases, creatinine, and creatine phosphokinase.

These post-vaccination symptoms are not recorded as adverse events (either associated with the study product administration or developing after discontinuation); they are registered by the participant in a diary and assessed by the physician as post-vaccination complications.

Transient flu-like syndrome should not be diagnosed as ARVI, in this case a PCR test for SARS-CoV-2 is not carried out.

If the participant develops COVID-19 or is hospitalized for COVID-19, then delayed telephone visit will be performed. The duration of the visit is determined by the study investigator on a case-by-case basis.

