 - drug products with thymus hormones;
 - herbal immunostimulants (immunal®, etc.).
- 3. Immunosuppressants (L04).
- 4. Antitumor drugs (L01) and antitumor hormonal drugs (L02).
- 5. Immune sera and immunoglobulins (J06).
- 6. Vaccines (J07).
- 7. Corticosteroids for systemic use (H02AB).
- 8. Any unapproved medicinal product.
- 9. Drugs that previously caused hypersensitivity/allergic reactions in patient.

Study design scheme

Schedule of study procedures

Procedure/ Visit	Visit 1 (Day 1)	Visit 2 (Day 22 + 3 days)	Unscheduled visit [*]	Visit 3 «phone» ▲ (Day 35 + 3 days)
Informed consent	+			
Registration in the IVRS and assignment of a personal code	+			
Rapid test for SARS-CoV-2 (COVID-19 Ag)	+	+		
Demographics	+			
Medical history	+			
Concomitant diseases and conditions	+	+	+	+
Concomitant therapy	+	+	+	+
Nasopharyngeal and oropharyngeal (throat) swabs for PCR diagnostics	+*	+*	+	
Pregnancy test	+			
Inclusion/exclusion criteria	+			
Randomization and prescription of study therapy	+			
E-diary supply	+	+	+	+
Study drug supply	+			

				17 0001 202	
Study drug accountability,		1			
compliance assessment		Т			
Evaluation of treatment safety	+	+	+	+	
Visit completion	+	+	+	+	
Study completion [•]					
* Conducted in case of a participant's illness with COVID-19					
▲ If the participant has had COVID-19	or has been hosp	italized for COVII	D-19, the timing of	the visit is	
determined by the study investigator of	n a case-by-case b	asis.			
	C GING G H A				

* Conducted with a positive rapid test for SARS-CoV-2 (COVID-19 Ag).

◆ If a patient falls ill with COVID-19, he or she will terminate participation in the study early.

Statistical Analyses

Samples

Total set: All subjects who signed Informed Consent Form (ICF). This sample will consider all adverse events (AEs) throughout the study, including those occurred prior to the study therapy.

The sample including all enrolled and randomized patients who received at least one dose of the study drug to be used for *analysis of the study treatment safety and tolerability* (*Safety population*), as all AEs identified after the study drug administration will be recorded.

The AEs registered in patients of the *Total set* sample from the moment of signing the Informed Consent Form, but before the test drug administration will not be taken into account when analyzing the study therapy safety.

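### Study drug accountability is planned only at Visit 2, so a symptomatic case confirmed earlier has no planned adherence value and is open to per-protocol exclusion because it reached the endpoint

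*Combined protocol and SAP*

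**What the plan says.** **Where adherence is measured.** In the Schedule of study procedures, the row beginning "Study drug accountability" carries one mark, in the column headed "Visit 2 (Day 22 + 3 days". The unscheduled-visit and telephone-visit cells are empty, and there is no early-termination column. The mark is damaged in the extracted text, but one empty cell (Visit 1) precedes it and none of the later cells is filled.

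**How a case is confirmed and what follows.** Under Study design, if ARVI symptoms appear within the five weeks, "then the study investigator performs an unscheduled visit, during which swabs are taken from the nasopharyngeal and oropharyngeal mucosa". Once infection is confirmed, "the participant prematurely completes the study as having reached the primary endpoint". Criteria for Withdrawal or Termination, item 2, says the same, as does a schedule footnote ("he or she will terminate participation in the study early"). For a participant who develops COVID-19, "then delayed telephone visit will be performed".

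**What the per-protocol rules do with it.** Under Statistical Analyses, the deviations that make data fully or partially invalid include item 4, "Increase or decrease of 25% or more in the amount of study therapy received", and item 5, "Inability to assess patient's objective compliance (adherence to therapy) according to the formula (e.g. loss of packaging". Participants whose data are invalid in this way are left out of the per-protocol set. That set also requires the full therapy and attendance at every planned visit. The formula named in item 5 is not given, and item 4 states no reference amount.

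**The concern.** A participant who stays free of infection reaches Visit 2 and has tablets counted. A participant who falls ill and is confirmed during the three treatment weeks leaves before the only planned count. Whether adherence is known, and so whether item 5 applies, then depends on the primary outcome.

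This matters because the per-protocol set is not a side analysis here. The required 570 per group is stated as a per-protocol number, and so is the interim at 485 per group. The documents do not say whether the per-protocol set or the Full Analysis Set is primary. If on-treatment cases drop out of the per-protocol set, the events that bear most directly on prevention during treatment are missing from it, and for those cases poor adherence cannot be told apart from lack of effect.

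**Working it through.** **1. The plan's own figure.** Inputs from Evaluation of sample size: placebo rate 0.03, Ergoferon rate 0.005, two-sided alpha 0.05, power 0.80, looks at 0.85 and 1 with O'Brien-Fleming boundaries.

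- OR = (0.005/0.995)/(0.03/0.97) = 0.162; ln(OR) = −1.817.
- Fixed-sample n per group = (1.960 + 0.842)² × [1/(0.03 × 0.97) + 1/(0.005 × 0.995)] / 1.817² = 559.4.
- Group-sequential inflation 1.01885 (final critical value 2.0255, as in the plan): 559.4 × 1.01885 = 570.0. The stated 570 is reproduced.
- Interim: 0.85 × 570 = 484.5, so 485, as stated.

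**2. Expected cases in 570 per group.** 570 × 0.03 = 17.1 placebo and 570 × 0.005 = 2.85 Ergoferon; total 19.95, about 20.

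**3. Ceiling on cases with no planned adherence value.** The documents do not give the timing of cases. Assume even risk over 35 days and every on-treatment case symptomatic and swabbed before Visit 2:

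- 19.95 × 21/35 = 11.97, about 12 (10.26 placebo, 1.71 Ergoferon).
- Timing: if 40% of cases fall in the first three weeks the ceiling is 0.40 × 19.95 = 8.0; if 80%, it is 16.0.
- Symptoms: a symptom-free participant is tested only at Visits 1 and 2, so an on-treatment case without symptoms is found at Visit 2, where compliance is assessed. If a share s of on-treatment cases is symptom-free, the even-risk figure becomes 12 × (1 − s); for example, s = 0.5 gives 6.

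**4. Does item 4 also exclude them?** Two tablets daily for 21 days is 42 tablets. If that full course is the reference, the 25% limit is reached at 0.75 × 42 = 31.5 tablets.

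- 15 complete days: 30 of 42, a shortfall of 28.6%; excluded.
- 16 complete days: 32 of 42, a shortfall of 23.8%; not excluded.

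So item 4 catches a fully adherent case only if fewer than about 16 days were completed, and only if the full course is the denominator.

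**5. What loss from the per-protocol set would mean.** Suppose a share f of cases leaves the set in both groups and 570 per group are still analysed. Each rate p becomes p(1 − f)/(1 − pf). The odds ratio stays at 0.162, but events fall. With the method of step 1:

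| f | Cases left (placebo, Ergoferon) | Power |
|---|---|---|
| 0 | 17.1, 2.9 | 0.80 |
| 0.2 | 13.8, 2.3 | 0.71 |
| 0.4 | 10.4, 1.7 | 0.59 |
| 0.6 | 7.0, 1.1 | 0.43 |

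This loss belongs to the per-protocol rules as a whole. The missing count is one route to it, alongside the requirements for full therapy and all visits.

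**The case against.** The strongest reply is that the missing mark changes little. Read literally, an early case already fails the per-protocol set because it has neither the full course nor every visit, whether or not tablets are counted. The Full Analysis Set has no compliance condition and keeps every such case, no adherence-response analysis is planned, and a randomised comparison in that set does not need to know who took tablets. The document is also a protocol summary: the formula in item 5 may treat early completers sensibly, and a site might count tablets anyway.

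Much of this stands. Adding the count alone would not return these cases to the per-protocol set, and the power figures cannot be charged to the schedule alone. But rewording the set definition alone fails too, because item 5 would still exclude a case with no compliance value. A definition can be clarified later; a count that was not made may not be recoverable. Nothing in the documents plans one.

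Three stronger readings are tempting and not supported:

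- That tablets go uncounted for every infection arising on treatment. Symptom-free cases are found at Visit 2, and infections confirmed after Visit 2 also have a value.
- That every early case breaches the 25% rule. Step 4 shows that a fully adherent case with 16 or more complete days does not.
- That the trial's efficacy result as a whole is compromised. The Full Analysis Set is unaffected, and the documents do not name the per-protocol set as primary.

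**Conclusion.** The point holds for symptomatic cases confirmed at an unscheduled visit before Visit 2. The plan schedules no adherence measurement for them, and item 5 then excludes them from the per-protocol set, with item 4 as a possible second route. Membership of that set therefore depends on the outcome. Under even risk over 35 days, with all on-treatment cases symptomatic, at most about 12 of about 20 expected cases are affected. The number falls as the symptom-free share rises, and the ceiling moves between 8 and 16 if 40% to 80% of risk falls in the treatment weeks. The defect itself does not depend on these assumptions; its size does. It should be corrected because the sample size and the interim are counted in per-protocol participants and the correction costs almost nothing. Retention of these cases in the Full Analysis Set keeps it from being more serious.

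**What to change.** Three changes, which work only together:

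1. In the Schedule of study procedures, mark accountability and compliance assessment at the unscheduled visit and at any early termination before Visit 2.
2. For items 4 and 5 of the per-protocol deviations, define compliance as tablets taken divided by tablets due, counted from Day 1 to the confirming swab or the end of treatment, whichever comes first.
3. State in the per-protocol definition that reaching the primary endpoint counts as having completed protocol therapy and scheduled visits. Without this, changes 1 and 2 do not keep the cases in the set.

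The cost is a short tablet count at a visit that already takes place, one CRF field and two sentences of text. The planned 570 per group and 485 at the interim do not change.
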